**Objectives and Endpoints – Phase 1a Dose Escalation/Exploration – FPT155 + Pembrolizumab:**

Objectives	Endpoints
Primary	

 
To evaluate the safety and tolerability of FPT155 in combination with pembrolizumab in patients with advanced non-small cell lung cancer
 
To determine the RD of FPT155 in combination with pembrolizumab in patients with advanced non-small cell lung cancer.
 
	
 
The incidence of adverse events (AEs), serious adverse events (SAEs), clinical laboratory abnormalities, and electrocardiogram (ECG) abnormalities
 
The incidence of dose limiting toxicities (DLTs)
 

Secondary	

 
To evaluate the preliminary clinical response rate of FPT155 in combination with pembrolizumab in patients with non-small cell lung cancer
 
	
 
Objective Response Rate (ORR), defined as the total number of patients with responses of either CR or PR, as determined by the investigator per RECIST v1.1, divided by the total number of patients who are evaluable for a response
 

Exploratory	

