#### 4.1.1.3 Dose Limiting Toxicity Definitions

The DLT evaluation interval begins on the first day of treatment upon start of infusion and continues for 21 days. Patients who receive at least 1 dose of study treatment and remain on study for the 21-day DLT evaluation interval or patients who discontinue study treatment for drug-related AEs before clearing the 21-day DLT evaluation interval will be considered evaluable for DLT determination.

DLTs during Phase 1a dose escalation are defined as any of the following deemed by the investigator as related to FPT155:

- Absolute neutrophil count (ANC)  $< 1.0 \times 10^9/L$  for  $> 5$  days duration or Grade 3 febrile neutropenia (eg, ANC  $< 1.0 \times 10^9/L$  with a single temperature of  $> 38.3^{\circ}C$  or fever  $> 38^{\circ}C$  for more than 1 hour)
- Platelets  $< 25 \times 10^9/L$  or platelets  $< 50 \times 10^9/L$  with clinically significant hemorrhage
- Aspartate aminotransferase (AST) or ALT  $> 3 \times$  upper limit of normal (ULN) with concomitant total bilirubin  $> 2 \times$  ULN not related to liver involvement with cancer
- Grade 3-4 non-hematological toxicity except:
  - Grade 3 fatigue  $< 7$  days
  - Grade 3 nausea and Grade 3-4 vomiting and diarrhea lasting  $< 72$  hours in patients who have not received optimal anti-emetic and/or anti-diarrheal therapy
  - Grade 3 endocrinopathy that is adequately treated by hormone replacement
  - Laboratory value that may be corrected through replacement within 48 hours
- Grade 2 neurological toxicity except headache and peripheral neuropathy in patients with Grade 1-2 peripheral neuropathy at entry

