#### Additional DLT Considerations for FPT155 in combination with pembrolizumab

Because pembrolizumab is a known immune checkpoint inhibitor and one of the proposed mechanisms of action of FPT155 is immune checkpoint blockade, immune-related adverse events (irAEs) are anticipated with this combination. An irAE is defined as a clinically significant AE that is associated with study drug exposure, without a clear alternate cause, and consistent with an immune-mediated mechanism. Based on that background, the first occurrence of the following irAEs will not be considered a DLT because they may occur with immune therapy and are likely to be fully reversible per [Appendix 8](#):

- Grade 3 tumor flare (defined as local pain, irritation, or rash localized at sites of known or suspected tumor)
- Grade 3 non-skin immune-related adverse event (irAE) that resolve to a Grade 1 or less within 14 days with management per [Appendix 8](#)
- Transient (resolving within 6 hours of onset) Grade 3 infusion-related AEs
- Grade 3 drug-related bronchospasm or anaphylactic or anaphylactoid reactions

Dose escalation may be paused prior to determining an MTD based on observed safety, tolerability, or emerging PK or PD results.

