### 6.9.3 Dose Modification and Delay Criteria

Dose reductions or delays for FPT155 may be permitted for patients on treatment beyond the DLT evaluation interval in Phase 1a dose escalation, any patients in the Phase 1a dose exploration, or any patients in Phase 1b per the guidelines in [Table 9](#). Dose reductions can be assessed using local laboratories. If a patient in Phase 1a dose escalation requires a dose reduction of FPT155 during the DLT period, they will be considered a DLT and be permanently discontinued from FPT155.

Dose reductions and delays for FPT155-related AEs or laboratory abnormalities should follow the guidelines outlined in [Table 9](#). Refer to Section [6.9.4](#) and [Appendix 10](#) for additional specific guidelines for irAEs and CRS. Any variations from these guidelines must be discussed with the Sponsor prior to dosing and must take into consideration the overall benefit and risks for the patient of continued participation in the study.

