**Table 9: Dose Modification and Delay Criteria for FPT155 (Non-Infusion Toxicity)**

FPT155-related Toxicity Grade	Dose Schedule	New FPT155 Dose
Grade 1	No delay or missed dose required	100% of dose
Grade 2	Delay or miss dose until recovery to Grade 1 for suspected irAEsa and CRSb No delay or missed dose required for other AEs	100% of dose
Grade 3 (first occurrence)	Delay or miss dose until recovery to baseline or Grade 1	If recovery to baseline or Grade 1 within 14 days, may resume at 100% of starting dose or 1 dose lower c
Grade 3 (second occurrence)	Delay or miss dose until recovery to baseline or Grade 1	If recovery to baseline or Grade 1 within 14 days, may resume at 1 level lower b than previous dose or discontinue
Grade 3 (third occurrence) Grade 3 which does not recover to baseline or Grade 1 within 14 days Any Grade 4	Permanently Discontinue	N/A

a Refer to Section 6.9.4 and [Appendix 8](#) for additional guidance regarding irAEs

b Refer to Section 6.9.5 and [Appendix 10](#) for additional guidance regarding CRS

c E.g., 1 dose level lower for patients treated at 70.0 mg is 42.0 mg; 1 dose level lower for patients treated at 42.0 mg is 21.0 mg.

Abbreviations: AE = adverse event; irAEs = immune-related adverse events; CRS = cytokine release syndrome.

The first dose of each cycle is considered Day 1 of each cycle. Cycles will repeat every 21 days unless there is a treatment delay. A treatment delay of longer than 4 weeks should be discussed with the medical monitor prior to continuation of that subject on study. Treatment is administered Q3W until disease progression, unacceptable toxicity, or until the patient meets any of the other protocol-specified withdrawal criteria.

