#### 6.9.4 Management of irAEs

Based on the underlying mechanism action, irAEs associated with the anti-CTLA-4 class of drugs (eg, ipilimumab) may potentially be observed with FPT155. Given the differentiated mechanism of action of FPT155 and the absence of any clinical data, the actual timing, incidence and severity of these AEs may differ significantly from anti-CTLA-4 therapies. General guidelines for management of suspected irAEs are provided here. These may be supplemented by discussions with the Sponsor as well as institutional guidelines on management of these toxicities.

In all instances, patients should be thoroughly evaluated to rule out a non-inflammatory etiology (eg, disease progression, concomitant medication, infections etc.). Symptomatic or topical therapy should be considered for most Grade 1 or 2 events unless otherwise specified in [Appendix 8](#). Corticosteroids are the primary therapy for irAEs. Corticosteroids should be tapered over at least 2-4 weeks in patients experiencing Grade 2 AEs and at least 4-8 weeks in

patients experiencing Grade 3/4 AEs. Appropriate antiviral, antifungal (e.g. pneumocystis) and antibacterial prophylaxis must be considered in patients receiving corticosteroids for prolonged durations to reduce the risk of opportunistic infections. More potent immunosuppressive agents such as TNF inhibitors (eg, infliximab) should be considered for events not responding to systemic steroids. Refer to [Appendix 8](#) for additional specific guidelines for individual irAEs.

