**APPENDIX 8: ALGORITHMS FOR EARLY DETECTION AND TREATMENT OF IMMUNE RELATED ADVERSE EVENTS (IRAES)**

The guidelines provided below have been adapted from the European Society for Medical Oncology (ESMO) clinical practice guidelines for management of toxicities from immunotherapy (Haanen 2018). Please refer to the full publication for management of irAEs not specifically discussed below (Appendix 9). These may be supplemented by discussions with the sponsor's medical monitor as well as institutional guidelines on management of these toxicities.

Diarrhea and Colitis			
Grade	FPT155 Dosing	Management Escalation Pathway	Assessment and Investigations
Grade 1 Diarrhea : <4 stools/ day over baseline Colitis : asymptomatic	No delay or missed dose	Symptomatic management: Oral fluids, loperamide, avoid high fiber/lactose diet Persists >14 days or worsens, treat as Grade 2	Close monitoring for worsening symptoms Patient education to immediately report worsening symptoms
Grade 2 Diarrhea : 4-6 stools per day over baseline; Outpatient management if appropriate Colitis : abdominal pain, blood in stool	Delay or miss dose Reinitiate upon recovery to $\leq$ Grade 1	Symptomatic management: Oral fluids, loperamide, avoid high fiber/lactose diet Persists > 3 days or worsens 0.5-1.0 mg/kg (methyl)prednisolone or oral equivalent Persists >3 days or worsens, treat as Grade 3/4	Clinical safety labs (eg, CBC, chemistry, CRP) Stool microscopy for leukocytes/ova/parasites, culture, viral polymerase chain reaction (PCR), clostridium difficile toxin, cryptosporidia
Grade 3/4 Diarrhea (G3) : $\geq$ 7 stools per day over baseline; incontinence; requires hospitalization Colitis (G3) : severe abdominal pain, fever, ileus, peritoneal signs; medical intervention indicated G4 : Life-threatening, perforation	Permanently discontinue FPT155	1.0-2.0 mg/kg (methyl) prednisolone IV or IV equivalent Persists > 3 days, infliximab 5 mg/kg (if no contraindication)	Assess as above Urgent gastrointestinal (GI) consult and abdominal CT and/or sigmoid/colonoscopy

Hepatitis			
Grade	FPT155 Dosing	Management Escalation Pathway	Assessment and Investigations
Grade 1 AST or ALT > ULN-3.0 x ULN and/or T. bili > ULN-1.5 x ULN	No delay or missed dose	N/A	Close monitoring for worsening symptoms or laboratory parameters

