4.3 DLT-Evaluable Population

All patients enrolled into Phase 1a dose escalation portion of the study who received at least 1 dose of all assigned study drug(s) and remain on study for the 21-day DLT evaluation period, or who experienced a DLT before clearing the 21-day DLT evaluation interval.

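### In the combination cohorts, a Grade 3 irAE that permanently ends FPT155 under Appendix 8 can be counted as a non-DLT in the 3+3

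*Protocol*

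**What the plan says.** **The exemption.** Protocol 4.1.1.3 (combination considerations), repeated in the synopsis, lists events whose first occurrence is not a DLT because they are expected with immune therapy and likely to reverse. One is a "Grade 3 non-skin immune-related adverse event (irAE) that resolve to a Grade 1 or less within 14 days with management per" Appendix 8. Nothing is carved out for events that end treatment.

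**Appendix 8.** The FPT155 dosing column reads "Permanently discontinue FPT155" in the Grade 3/4 rows for diarrhea/colitis, hepatitis and pneumonitis, with no exception for fast recovery. Grade 3 renal events may restart on recovery. So may Grade 3/4 skin events, although permanent discontinuation is also an option there.

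**Table 9.** After a first Grade 3 event that recovers within 14 days, the patient "may resume at 100% of starting dose or 1 dose lower". But 6.9.3 sends irAEs to 6.9.4, and 6.9.4 points to Appendix 8 "for additional specific guidelines for individual irAEs".

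**Who is counted.** Under 4.1.1.3, "patients who discontinue study treatment for drug-related AEs before clearing the 21-day DLT evaluation interval will be considered evaluable for DLT determination". SAP 4.3 includes patients who "remain on study for the 21-day DLT evaluation period", or who had a DLT earlier.

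**Dose reductions.** Section 6.9.3: "If a patient in Phase 1a dose escalation requires a dose reduction of FPT155 during the DLT period, they will be considered a DLT".

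**Use of the count.** DLT incidence is a primary endpoint of the combination part (Protocol 3.0), and 4.1.4 applies the 3+3 to combination escalation.

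**The concern.** The exemption leans on Appendix 8 as the route to reversibility, yet for three major irAEs Appendix 8 takes the patient off FPT155 permanently. Such a patient stays in the 3+3 denominator and adds nothing to the numerator. Three combination patients could be recorded as 0/3 although one or more can never receive FPT155 again.

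That sits badly with two other statements. Section 4.5 justifies the 3+3 by the aim of not selecting a dose whose treatment-limiting toxicity exceeds 17%, and a toxicity that permanently ends the drug is treatment-limiting on any plain reading. Section 6.9.3 makes a required dose reduction in the same window a DLT, so the milder consequence counts and the more severe one may not.

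At stake are the number that permits escalation and the DLT incidence reported as a primary endpoint.

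**Working it through.** **1. The texts side by side (combination cohorts, first occurrence, Grade 3, resolved to Grade 1 or less within 14 days)**

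| Event | Exempt under 4.1.1.3? | FPT155 after recovery, Appendix 8 |
|---|---|---|
| Diarrhea/colitis | Yes | Permanently stopped |
| Hepatitis | Yes | Permanently stopped |
| Pneumonitis | Yes | Permanently stopped |
| Renal | Yes | May restart |
| Skin | No | May restart, or stop |

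The exemption covers three events after which FPT155 cannot restart and leaves out skin, where it can. Grade 4 and unresolved events are outside this bullet. The documents do not say whether the exemption overrides the separate transaminase-plus-bilirubin DLT criterion.

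**2. The plan's own figure.** The highest observed rate at which Table 6 still permits escalation is 1/6 = 16.7%, which rounds to the 17% in 4.5.

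**3. Effect on the count.** Let r be the true 21-day rate of FPT155-related events that would otherwise be DLTs, f the share of them that is exempt but treatment-ending, and p = r(1 − f) the counted rate, with no other DLTs. A level clears on 0/3, or on 1/3 followed by 0/3:

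P(clear) = (1 − p)³ + 3p(1 − p)⁵

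The documents give neither r nor f for this combination, so both are assumptions. Example, r = 0.10 and f = 0.20: p = 0.08, and 0.92³ + 3 × 0.08 × 0.92⁵ = 0.779 + 0.158 = 0.937.

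| r | all counted (f = 0) | f = 20% | f = 50% | f = 80% |
|---|---|---|---|---|
| 5% | 97.3% | 98.3% | 99.3% | 99.9% |
| 10% | 90.6% | 93.7% | 97.3% | 99.5% |
| 17% | 77.3% | 84.1% | 93.0% | 98.7% |

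At f = 20% the rise is 1.0, 3.1 and 6.8 percentage points.

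**4. A clean count hiding an exempt event.** P(counted 0/3 with at least one exempt event) = (1 − p)³ − (1 − r)³. At f = 50% this is 7.0%, 12.8% and 19.4% for r = 5%, 10% and 17%.

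**5. Where the truth probably lies.** To be exempt and treatment-ending, an event must be Grade 3, a first occurrence, in one of three organs, and resolved within 14 days; to matter for the count, it must also start within 21 days. The guideline reproduced in Appendix 9 says ipilimumab toxicities usually start within the first 8 to 12 weeks. It gives a median onset of 2.8 months for pneumonitis and 3 months for GI symptoms on anti-PD-1, and says hepatitis usually takes 4 to 6 weeks to resolve. It also says onset may be earlier with combined checkpoint blockade. On balance this favours low r and low f, so the 50% and 80% columns are an upper range.

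**6. Cost of counting these events.** P(expand to 6) = 3p(1 − p)². Going from f = 50% to f = 0:

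| r | f = 50% | f = 0 | extra expansions over 5 levels | extra patients (× 3) |
|---|---|---|---|---|
| 5% | 7.1% | 13.5% | 0.32 | 1.0 |
| 10% | 13.5% | 24.3% | 0.54 | 1.6 |
| 17% | 21.3% | 35.1% | 0.69 | 2.1 |

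Five levels assumes a start two levels below 560 mg: 140, 280, 560, 840 and 1260 mg, all opened.

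**The case against.** The strongest reply is that no rule is broken. Section 4.1.1.3 classifies an event for the count and Appendix 8 says how to dose afterwards, so a site can follow both. Section 4.1.1.6 foresees discontinuations that fall short of a DLT and weighs them in choosing the RD. This stands. A reader might infer that the two texts contradict each other outright; the documents do not support that. The inconsistency is one of purpose.

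A reader might also infer a live clash between Table 9 and Appendix 8. Sections 6.9.3 and 6.9.4 already route irAEs to Appendix 8, so Table 9 is secondary. The guidance also allows variations after discussion with the sponsor.

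The comparison with dose reductions is weaker in practice than on paper. With dosing every 3 weeks and a 21-day window, a patient normally receives one FPT155 dose in it, so a reduction there is rare. The rule still shows which way the protocol leans.

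Exempting reversible irAEs is a legitimate choice, and the 17% statement concerns the dose finally selected, not each cohort. Section 4.1.1 bases escalation on overall safety as well as DLTs, 4.1.1.1 lets the CRC ask for more evaluation at a dose, 4.1.1.3 allows a pause, and SAP 6.3.1.6 tabulates TEAEs leading to FPT155 discontinuation. All of this mitigates. None of it changes the Table 6 count or the reported DLT incidence.

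**Conclusion.** The point holds as an inconsistency of purpose with a real effect on the formal 3+3 count and on a primary endpoint of the combination part, and it should be corrected. A FPT155-ending toxicity in Cycle 1 can be scored as no DLT. The patient is evaluable under 4.1.1.3 and is in the SAP DLT-evaluable set if still on study at Day 21.

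The size is unknown and probably small. With 20% of events exempt, clearance of a level rises by about 1 percentage point at a 5% true rate and 3 at 10%. It rises by more only with a larger exempt share or a higher true rate. These figures assume independent patients, no other DLTs, and values of r and f that the documents do not supply.

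A reader might infer from the upper range that the trial would escalate past toxic doses unchecked. That does not follow: the probabilities describe the count, 0/3 permits escalation without compelling it, and the CRC sees all the safety data.

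**What to change.** In Protocol 4.1.1.3 and the synopsis, add to the bullet: *unless the event requires permanent discontinuation of FPT155 under Appendix 8, in which case it is a DLT*. The exemption then survives wherever FPT155 may restart, for example after Grade 3 renal events.

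If the sponsor does intend restart after recovered Grade 3 diarrhea/colitis, hepatitis or pneumonitis, amend the Grade 3 rows of Appendix 8 instead.

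Either way, carry the final combination DLT text into SAP 2.2.4. SAP 2.2.1 lists the DLT criteria without the combination exemptions and 2.2.4 adds none. This is a consistency edit only.

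The drafting cost is one clause in two places, or three table rows, plus the SAP edit. Adding the clause means slightly more cohorts expand to 6: about 1 to 2 extra patients over five levels at true rates of 5% to 17% with half of events otherwise exempt. That fits the approximate cap of 30, but with little slack: five levels fully expanded use 5 × 6 = 30, leaving no room for replaced patients (7.4), intermediate levels or a lower starting dose (4.1.4).

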#### 4.1.1.4 Dose Escalation Decisions in Phase 1a FPT155 Monotherapy

An initial accelerated titration design enrolling at least 1 patient at each dose level is planned for FPT155 dose levels 0.07, 0.21, 0.70, and 2.1 mg. Dose escalation to the next dose level may proceed after at least 1 patient completes the 21-day DLT evaluation interval.

If a single patient experiences a DLT during the 21-day DLT evaluation interval, standard 3+3 dose escalation criteria will apply for that cohort with enrollment of additional patients. All subsequent dosing cohorts will then follow standard 3+3 dose escalation criteria.

Alternatively, if 2 patients experience moderate AEs (at any planned accelerated titration dose level), standard 3+3 dose escalation criteria will apply for the highest dose level at which a moderate AE was experienced, with enrollment of additional patients. All subsequent dosing cohorts will then follow standard 3+3 dose escalation criteria. Moderate AEs are defined as  $\geq$  Grade 2 AEs deemed by the investigator as related to FPT155. Grade 2 laboratory values will not be considered as moderate AEs for this purpose unless accompanied by clinical sequelae.

If not already applied at a lower dose level according to the criteria stated above, enrollment at all dose levels  $\geq$  7.0 mg will follow a standard 3+3 dose escalation design.

The algorithm outlined in [Table 6](#) below will be used for all dose escalation decisions.

**Table 6: Algorithm for 3+3 Dose Escalation Decisions**

Number of Patients with DLT at a Given Dose Level	Dose Escalation Decision Rule
0/3 or 1/6	Enroll 3 patients at next dose level (next/higher cohort)
1/3	Enroll 3 additional patients at current dose level (current cohort)
$\geq 2$	Stop enrollment. If at the starting dose level, the study will be stopped. If at any other dose level, enroll 3 more patients at the previous dose level (previous/lower cohort) if only 3 were previously enrolled, or at an intermediate dose level

Abbreviations: DLT = dose limiting toxicity.

#### 4.1.1.5 Dose Escalation Within a Cohort

In Phase 1a dose escalation, intra-patient dose escalation will be permitted in patients enrolled at dose levels below 70 mg, provided:

- The patient did not experience a DLT
- All other AEs have recovered to Grade 1 or lower prior to dose escalation
- The patient may only dose escalate by a maximum of 1 dose level every 21 days and only after that dose level has cleared DLT review by the CRC (eg, a patient enrolled at 0.07 mg may escalate to 0.21 mg only after the 0.21 mg dose level has been cleared by the CRC).
- The patient cannot dose escalate beyond the 70 mg dose level

Intra-patient dose escalation will only be permitted after a discussion between the Sponsor and investigator, taking into account the overall safety experience, PK, and PD data available at the time of the request. Safety data from such patients will be reviewed as part of the overall safety and tolerability of FPT155.

#### 4.1.1.6 Determination of Recommended Dose and Maximum Tolerated Dose

The maximum tolerated dose (MTD) will be defined as the dose level below that in which  $\geq 2$  DLTs are identified. If dose escalation completes without the identification of 2 DLTs at a given dose level, no MTD will have been identified. The Sponsor may discontinue dose escalation prior to determining a MTD based on the available observed safety, tolerability, PK and PD. The RD of FPT155 will be identified based on an evaluation of all available safety, tolerability, PK, and PD data. The determination of RD will consider toxicities observed both during and beyond the DLT evaluation period as well as dose reductions and discontinuations due to toxicity that do not meet the DLT criteria. The RD, therefore, may or may not be the same as the MTD but cannot be higher than the MTD.

#### 4.1.2 Phase 1a FPT155 Monotherapy Dose Exploration

Phase 1a dose exploration consists of up to approximately 50 patients in total who may be enrolled at one or more dose levels to further evaluate safety, PK, PD, and clinical activity (conditional upon the dose level clearing dose escalation criteria). Toxicities observed in these patients will contribute to the overall assessments of safety and tolerability, and may inform selection of the RD. The Sponsor may choose to evaluate clinical activity in specific tumor types based on emerging safety, PK, PD, and efficacy data.

Intensive monitoring will occur in the outpatient setting and include a minimum 6-hour observation window following completion of the first and second infusions. There will be an interval of at least 24 hours between administration of the first dose in each patient.

